- Dose escalation decisions will also take into account all available data. This includes, but is not limited to the safety and PK characteristics of all cohorts assessed. In addition, dose escalation decisions will be determined by the N-CRM [Neuenschwander, 2008]. The FACTS will be used to conduct the N-CRM. These decisions will occur following review of these data by the investigator(s), GSK medical monitor, CPMS representative, and statistician. The decision and rationale will be documented in written format and distributed to the investigator(s), GSK medical monitor, CPMS representative, and statistician.
- Dose adjustments/stopping criteria will adhere to guidelines provided in Section 3.10.
- Subjects will receive GSK2857916 in this weekly dosing cohort until disease progression, unacceptable toxicity, withdrawal of consent, or completion of the pre-specified treatment period of 48 doses (16 cycles on Schedule 2).
- If a subject misses a dose on the weekly schedule, the dose will be recorded as missing and the next dose will be administered according to the current cycle. The counting of days and cycles will continue regardless of whether or not the subject received the dose. Dose delays of + 3 days are allowed in order to accommodate scheduling conflicts/holidays, etc.

Additional alternative schedules may be evaluated based on emerging data. If an alternative schedule other than the weekly dosing schedule is evaluated, details on dosing and Time and Events will be updated in the Study Procedures Manual (SPM).

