3.3.3. Dose-Limiting Toxicity - Part 1 only

Any subject in Part 1 (Dose Escalation) who received at least one dose of the drug (regardless of schedule) will be evaluated for DLTs. Safety data together with DLTs will be reviewed during the dose escalation meetings prior to opening enrollment into subsequent cohorts (see Section 12.1).

Subjects who have been withdrawn from the study for reasons other than toxicity but prior to completion of DLT observation period will be replaced. An event will be considered a DLT if its relationship to the investigational agent cannot be ruled out occurs within the DLT reporting period (first 21 days of treatment for schedule 1, and first 28 days for schedule 2) and meets one of the following criteria:

- Albuminuria ≥ 2000 mg/24 hr which has been confirmed by repeat test at least 7 days apart and is not considered to be related to disease progression based on consultation of investigator with GSK medical monitor
- Grade 4 neutropenia (without fever) lasting ≥ 7 days
- Febrile neutropenia lasting ≥ 72 hours
- Grade ≥ 3 thrombocytopenia associated with bleeding where estimated blood loss is > 10 mL or Grade 4 thrombocytopenia lasting > 7 days and not responding to platelet transfusions
- Any Grade 3 or greater non-hematologic toxicity as described in Common National Cancer Institute-Terminology Criteria for Adverse Events (NCI-CTCAE) version 4.0 [NCI, 2009] with the exception of the following Grade 3 events that can be controlled within 48 hours with routine supportive measures
 - Nausea and vomiting that can be controlled with anti-emetics
 - Diarrhea that can be controlled with anti-diarrheals
 - Rash or other skin reactions that can be controlled with antihistamines and steroids
 - Clinically asymptomatic electrolyte abnormalities which can be corrected within 48 hours)
- Liver toxicity meeting pre-specified GSK liver stopping criteria (see Liver in Section 3.9.1)

Tumor lysis syndrome does NOT constitute a DLT (Section 3.9.7).

A subject who develops a DLT will be allowed to stay on study only if the toxicity did not meet stopping criteria and recovered to \leq Grade 1 within 14 days, or after a longer recovery time if benefit to subject can be demonstrated and if the investigator and medical monitor agree that for a given subject the benefits may outweigh the risks.

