3.10.2. Predicted Toxicities and Proposed Dose Adjustments/Stopping Criteria

Toxicity	Grade/symptoms	Recommendations
Creatinine elevation which cannot be explained by concomitant sepsis, other severe infection with fever or dehydration	If absolute serum creatinine increase from baseline of > 0.3 mg/dL (26 µmol/L) but ≤ 0.5 mg/dL (44 µmol/L)	Repeat within 48 hours 
 If creatinine returns to ≤ 0.3 mg/dL (26 µmol/L) above baseline 
 Continue GSK2857916 at current dose If creatinine remains elevated: > 0.3 mg/dL (26 µmol/L) but ≤ 0.5 mg/dL (44 µmol/L) from baseline 
 Continue GSK2857916 Monitor creatinine at least weekly Consider 25% dose reduction if creatinine remains elevated (after discussion with Medical Monitor)
	If absolute serum creatinine increase from baseline of > 0.5 mg/dL	Repeat within 48 hours: 
 If confirmed: withhold therapy, institute treatment and monitoring as clinically indicated, and follow for resolution Discuss any further dosing with Medical Monitor* 
* Medical Monitor should consult GSK's nephrotoxicity panel about plans to continue therapy

Serum creatinine ≥ Grade 3	>3.0mg/dL from baseline or 3.0-6.0xULN	
 Provide appropriate medical treatment. Permanently discontinue treatment with GSK2857916

Toxicity	Grade/symptoms	Recommendations
Albuminuria	>2000mg/24 hr	
 • Re-test (at least 7 days apart). 
 ○ If not confirmed, continue GSK2857916 at 100% dose ○ If confirmed on re-test and no clear evidence of disease progression* 
 ▪ Interrupt treatment with GSK2857916 ▪ Repeat testing within 4 weeks 
 • If albuminuria \leq2000mg/24hr may restart GSK2857916 with 25% dose reduction • If albuminuria remains >2000mg/24hr after 4 weeks; Permanently discontinue GSK2857916 and withdraw subject from study; provide treatment as clinically indicated and follow for resolution 
* Medical Monitor should consult GSK's nephrotoxicity panel about plans to continue therapy

Thrombocytopenia	Grade 3: >25 and <50x10 ⁹ /L	
 • Where estimated blood loss is \geq 10 mL: withhold the treatment: • No bleeding: continue treatment with 25% dose reduction

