7.1.1. Dose Escalation

7.1.1.1. Every 3 Weeks Dosing Schedule for Multiple Myeloma

Time and Events Table for Full Study (Cycle = 21 days)									
Study Assessments ¹	Screen ²	Day 1 C1	Day 2 C1	Day 8 C1	Day 15 C1	Day 1 C2	D1 of C3-C16	End of Study Treatment	3-Month Off-study Follow-up
Informed Consent	X								
Baseline Demographics	X								
Medical History	X								
Physical Exam	X	X				X	At the start of each cycle	X	
Ocular Exam	X ³					X ⁴	At the start of each cycle ⁴	X ⁴	
ECOG Performance Status	X					X	At the start of each cycle	X	
Vital Signs (BP, HR, Body Temperature)	X	X ⁵		X	X	X ⁵	At the start of each cycle ⁵	X	
Weight and Height	X	Weight only				Weight only	Weight only - At the start of each cycle	Weight only	
Hematology	X	X ⁶		X	X	X	At the start of each cycle	X	
Clinical chemistry	X	X ⁶	X	X	X	X	At the start of each cycle	X	
Urine Dipstick	X	X ⁶				X	At the start of each cycle	X	
INR, PTT	X	X ⁶		X	X	X	At the start of each cycle		
HBV/HCV tests	X								
CK-MB, Troponin	X ⁷			X ⁷		X ⁷	At the start of each cycle ⁷	X ⁷	
BNP	X ⁸								
UPEP and urine Immunofixation	X					X	At the start of each cycle		
SPEP and serum Immunofixation, Serum M- protein Calculation	X					X	At the start of each cycle		
Kappa, lambda free LC, FLC ratio	X					X	At the start of each cycle		
24 hr urine protein and albumin	X					X	At the start of each cycle		

Time and Events Table for Full Study (Cycle = 21 days)									
Study Assessments ¹	Screen ²	Day 1 C1	Day 2 C1	Day 8 C1	Day 15 C1	Day 1 C2	D1 of C3-C16	End of Study Treatment	3-Month Off-study Follow-up
IgG, IgM, IgA	X					X	At the start of each cycle		
CRP, beta2 microglobulin	X					X	At the start of each cycle		
Pregnancy Test	X ⁹						At the start of cycles 5 ⁹ , 9 ⁹ , 13 ⁹	X ⁹	X ¹⁰
Chest X-ray	X								
12-lead ECG	X ¹¹	X ¹¹		X ¹¹	X ¹¹	X ¹¹	At the start of each cycle ¹¹	X ¹¹	
LVEF and valves assessment (ECHO)	X ¹²						At the start of cycles 4 ¹² , 9 ¹²	X ¹²	
Extramedullary plasmacytoma imaging	X ¹³						At the start of cycles 5 ¹³ , 9 ¹³ , 13 ¹³	X ¹³	
BM Aspirate (see below for each test required within procedure):									
Disease assessment	X ¹⁴						At the time of Complete Response		
BCMA assessment and PD (flow)	X ¹⁵			X ¹⁵					
FISH testing	X ¹⁶								
BM biopsy for disease assessment and BCMA expression (IHC)	X ¹⁷						At the time of CR (disease assessment only)		
Serum (soluble BCMA)		X ¹⁸	X ¹⁸	X ¹⁸	X ¹⁸	X ¹⁸	Predose at the start of each cycle	X ¹⁸	

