Serum (cytokines/chemokines)		X ¹⁹	X			X ¹⁹	At predose and EOI on D1 of each cycle	X	
Serum (anti-drug-antibodies)	X					X ²⁰	At the start of cycles 3 ²⁰ , 6 ²⁰ , 9 ²⁰ , 12 ²⁰ and 16 ²⁰	X	
Plasma-cfDNA	X							X	
Peripheral blood (flow for TBNK)	X ¹⁵					X ¹⁵	At the start of each cycle ¹⁵	X ¹⁵	
Serial Pharmacokinetics (blood)		X ²¹	X ²¹	X ²¹	X ²¹	X ²¹	C3D1 only ²¹	X ²²	
Urine PK	X ²³					X ²³	Day 1 of cycles 4 ²³ , 7 ²³ , 10 ²³ , 13 ²³ , 16 ²³		
Premedication if needed		X				X	At the start of each cycle		
GSK2857916 administration		X ²⁴				X ²⁴	X ²⁴		
Steroid eye drops		X ²⁵				X ²⁵	X ²⁵		
Adverse Events							Continuous		

Time and Events Table for Full Study (Cycle = 21 days)										
Study Assessments ¹	Screen ²	Day 1 C1	Day 2 C1	Day 8 C1	Day 15 C1	Day 1 C2	D1 of C3-C16	End of Study Treatment	3-Month Off-study Follow-up	
Concomitant Medications	X	Continuous								
Survival Status									X ²⁶	
Subsequent Treatment									X ²⁶	

- Assessments scheduled on days of dosing should be done prior to drug administration, unless otherwise specified. All other assessments can be ± 3 days of scheduled occurrence unless otherwise specified.
- All Screening assessments must be performed within 14 days prior to first dose unless otherwise specified. Informed Consent must be signed before any study-specific assessments are performed.
- Screening examination to include BCVA (best-corrected visual acuity), slit lamp examination (with special focus on cornea), intraocular pressure, and dilated fundoscopic examination may be performed within 21 days prior to first dose.
- On-study exams to include BCVA (best-corrected visual acuity) and slit lamp examination (with special focus on cornea); window for exams is up to 3 days prior to dosing.
- On initial (first infusion) dosing day, vital signs must be assessed at pre-dose (within 30 minutes prior to SOI), +10 minutes and +30 minutes (± 5 min) after SOI, EOI, and 1 hour post EOI. On subsequent dosing days, vital signs must be assessed at pre-dose (within 30 minutes prior to SOI), +30 minutes after SOI, and EOI. The Sentinel Subject must be observed for at least 24 hours post EOI. **On days where vital sign timepoints align with PK sampling timepoints, vital signs should be assessed prior to PK samples being drawn.**
- If completed within 72 hrs prior to the first dose, this assessment need not be repeated on Day 1 of Cycle 1. Refer to [Table 15](#) for comprehensive list of lab tests.

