19. Collect cytokines at predose (within 30 minutes prior to SOI) and EOI (± 5 min) (even when infusion is interrupted or halted) to assess allergic reaction)
20. All ADA samples will be collected prior to each infusion
21. PK samples to be taken (in all subjects) for both GSK2857916 and cys-mcMMAF measurement: C1D1 at pre-dose (within 30 minutes prior to SOI), 0.5 h after the start of the infusion (SOI) (± 5 min), at the end of infusion (EOI) just before EOI, 1 h after EOI, 3 h after EOI (± 5 min), 8 h after EOI (± 15 min), 24h after EOI (± 1 h) (Day 2); C1D8 1 sample; C1D15 1 sample; C2D1, at pre-dose (within 30 minutes prior to SOI) and at the EOI (just before EOI); C3D1 at pre-dose (within 30 minutes prior to SOI) and at the EOI (just before EOI).
22. Collect 1 PK sample at each subject's final visit.
23. Pre-specified amounts of urine will be collected for PK analysis from the 24 hour urine collection at Screening, C2D1, C4D1, C7D1, C10D1, C13D1, and C16D1. Refer to Section 7.4.2 for details.
24. Study drug administration ± 3 day window only
25. Prophylaxis with prednisolone phosphate 1% or dexamethasone 0.1% 1 drop QID x 4 days starting 1 day prior to treatment
26. Record subject's survival status and whether subsequent treatment for disease was given. Subject does not need to come in for visit.

Abbreviations:

ADA = Antibody Drug Antibody; ALP = alkaline phosphatase; BCVA = best corrected visual acuity; BNP = B-type natriuretic peptide; C1D1 = Cycle 1 Day 1, etc.; cfDNA = Circulating free DNA; CK = creatinine kinase; CRP = C-reactive protein; EM = extramedullary; EOI = End of Infusion; FLC = free light chain; PD = Pharmacodynamics; PK = Pharmacokinetics; QID = 4 times a day; SOI = start of infusion; SPEP = serum protein electrophoresis; UPEP = urine protein electrophoresis

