20. Collect cytokines at predose (within 30 minutes prior to SOI) and EOI (\pm 5 min) (even when infusion is interrupted or halted) to assess allergic reaction
21. All ADA samples will be collected prior to each infusion
22. PK samples to be taken (in all subjects) for both GSK2857916 and cys-mcMMAF measurement: C1D1 at predose (within 30 minutes prior to SOI), 0.5 h after the start of the infusion, at EOI (just before EOI), 1 h after EOI (\pm 5 min), 3 h after EOI (\pm 5 min), 8 h after EOI (\pm 15 min), and 24h after EOI (\pm 1 h) (Day 2); C1D8 at predose (within 30 minutes prior to SOI), and at EOI (just before EOI); C1D15 at predose (within 30 minutes prior to SOI) and at EOI (just before EOI); C2D1 at predose (within 30 minutes prior to SOI), at EOI (just before EOI); C3D1 at predose (within 30 minutes prior to SOI) and at EOI (just before EOI).
23. Collect 1 PK sample at each subject's final visit.

24. Pre-specified amounts of urine will be collected for PK analysis from the 24 hour urine collection at Screening, C2D1, C4D1, C7D1, C10D1, C13D1, and C16D1. Refer to Section 7.4.2 for details.
25. Study drug administration ± 1 day window only.
26. Prophylaxis with prednisolone phosphate 1% or dexamethasone 0.1% 1 drop QID x 4 days starting 1 day prior to treatment
27. Record subject's survival status and whether subsequent treatment for disease was given. Subject does not need to come in for visit.

Abbreviations:

ADA = Antibody Drug Antibody; ALP = alkaline phosphatase; BCVA = best corrected visual acuity; BNP = B-type natriuretic peptide; C1D1 = Cycle 1 Day 1, etc.; cfDNA = Circulating free DNA; CK = creatinine kinase; CRP = C-reactive protein; EM = extramedullary; EOI = End of Infusion; FLC = free light chain; PD = Pharmacodynamics; PK = Pharmacokinetics; QID = 4 times a day; SOI = start of infusion; SPEP = serum protein electrophoresis; UPEP = urine protein electrophoresis

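### On the scheduled Part 1 urine collections, a confirmed albuminuria DLT cannot be in hand at an escalation meeting held when the DLT period ends, and Section 3.3.3 does not settle whether a C2D1 value counts toward cycle 1

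*Protocol*

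**What the plan says.** Section 3.3.3 requires a DLT to occur within the reporting period, "first 21 days of treatment for schedule 1, and first 28 days for schedule 2", and to meet one of the listed criteria. One criterion is "Albuminuria ≥ 2000 mg/24 hr which has been confirmed by repeat test at least 7 days apart", provided it is not judged to be disease progression.

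In the escalation tables (7.1.1.1 and 7.1.1.2) the row "24 hr urine protein and albumin" is marked at screening, at C2D1 and at the start of each later cycle. It has no entry in cycle 1. Footnote 1 adds "Assessments scheduled on days of dosing should be done prior to drug administration, unless otherwise specified", so the C2D1 collection precedes the second cycle's first dose. The dosing windows are "Study drug administration ± 3 day window only" on Schedule 1 and "Study drug administration ± 1 day window only" on Schedule 2. Section 3.3.2 also allows, for the weekly schedule, "Dose delays of + 3 days are allowed in order to accommodate scheduling conflicts/holidays, etc".

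Section 12.1 schedules the dose escalation meeting for the end of each cohort's DLT period, with decisions resting on at least one cycle of safety data. Section 3.3.1.1 says the N-CRM uses whatever DLT information exists at each dose assignment. For albuminuria above the limit, Section 3.10.2 interrupts treatment only "If confirmed on re-test and no clear evidence of disease progression".

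**The concern.** Nephrotoxicity is the first risk listed in Section 1.3.1, and the animal renal changes came with albuminuria. The sponsor made albuminuria a named DLT accordingly. The DLT window, the urine schedule and the meeting date, each fixed in the protocol, do not fit together. A subject whose albumin rises during cycle 1 is first measured on the boundary of the window and confirmed after it.

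Two things are at stake. The next dose may be assigned while the event is at best unconfirmed. Two reviewers may also code the same subject differently in the model, because 3.3.3 does not say whether a nominal Day 22 or Day 29 pre-dose value belongs to cycle 1, or whether a repeat after the period confirms a cycle 1 event. The 24-hour collection sharpens the first question: one that finishes just before dosing on Day 22 began on Day 21.

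**Working it through.** **Inputs.** DLT period: Days 1–21 or 1–28 (3.3.3). Confirmation gap: 7 days or more (3.3.3). First post-dose collection: C2D1, pre-dose (7.1.1.1, 7.1.1.2). Dosing window: ±3 days on Schedule 1, ±1 day on Schedule 2 (footnotes to those tables). Baseline albuminuria must be at or below 500 mg/24 hr (Table 14), so the screening value cannot serve as the first of two positives.

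**Formulas.** C2D1 = cycle length + 1, shifted by the window. Earliest confirmation = C2D1 + 7. Overrun = earliest confirmation − last day of the DLT period.

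| | Schedule 1 | Schedule 2 |
|---|---|---|
| C2D1 | 21 + 1 = Day 22 (19–25) | 28 + 1 = Day 29 (28–30) |
| Earliest repeat | 22 + 7 = Day 29 (26–32) | 29 + 7 = Day 36 (35–37) |
| DLT period ends | Day 21 | Day 28 |
| Overrun | 29 − 21 = 8 days (5–11) | 36 − 28 = 8 days (7–9) |

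If the +3-day allowance in 3.3.2 applied to C2D1 on Schedule 2, C2D1 would be Day 32, the repeat Day 39 and the overrun 11 days. In the other direction, stacking a further 3-day early assessment window on the dosing window gives Day 19 − 3 + 7 = Day 23 and Day 28 − 3 + 7 = Day 32, still after the period ends. For confirmation inside the period, the first positive would have to fall by Day 21 − 7 = 14, or Day 28 − 7 = 21. The urine dipstick is scheduled at screening, C1D1 and C2D1, so no scheduled post-dose urine test in cycle 1 would prompt an earlier 24-hour collection.

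**Does the missing event change the recommended dose?** This part is illustrative, because the model's reference dose is not stated. Model: logit p = α + β·ln(dose/reference), with the prior in Section 13.2.1 (α mean −1.3281, SD 1.7153; ln β mean −0.795, SD 1; correlation −0.9352). The decision rule follows 3.3.1.2.1: highest posterior probability of a DLT rate in 16–33%, among doses whose probability of 33% or more is below 25% and which are no more than twice the current dose. I assumed reference doses of 0.96, 1.2, 1.5, 1.92 and 2.8 mg/kg and placed a cohort of 3 at each of seven planned levels from 0.12 to 3.6 mg/kg, giving 35 cases.

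| Cases (of 35) in which the recommendation changes | 0/1 at every lower level | 0/3 at the level just below |
|---|---|---|
| Albuminuria is the only DLT (1/3 against 0/3) | 6 | 4 |
| Cohort has one other DLT (2/3 against 1/3) | 35 | 32 |

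With 0/1 at every lower level, all 6 only-DLT changes are at 1.92, 2.8 or 3.6 mg/kg and only with a reference dose of 0.96 or 1.2. None occurs at 0.12–0.96 mg/kg. I attach no probability to these cases: the protocol gives no albuminuria rate, and the Table 5 medians are for any DLT. Nothing was computed for Schedule 2, which uses a separate model and increments of at most 30%.

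**The case against.** The strongest reply is that confirmation belongs to the criterion and not to the window. Other listed DLTs work that way: Grade 4 neutropenia must last 7 days or more, and the liver stopping criteria include an ALT elevation persisting 4 weeks, which cannot finish within 21 days. Onset in the window with later confirmation is the reading that makes the whole list usable. I accept that as the natural reading. It leaves open whether a nominal C2D1 value has its onset in cycle 1, and it does not make the confirmed event available at the meeting.

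Second, there are real safeguards. Escalation decisions must take account of all available data (3.3.1.1). Safety Update Meetings are held every three weeks in Part 1 (12.1). A confirmed event classed as a DLT enters the next N-CRM update. Clinical chemistry, including creatinine, is drawn on Days 2, 8 and 15 of cycle 1, and creatinine rises have their own hold rules (3.10.2). Urine can be collected more often if clinically indicated (1.3.1), and the sponsor may alter assessment timing (Section 7). The one-cycle minimum in 12.1 permits waiting. These lower the stakes, but none requires a cycle 1 albumin test, settles attribution or obliges the team to wait.

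Third, the text of this amendment suggests that Schedule 1 escalation is already finished: Part 2 opens only after Schedule 1 enrollment is complete (3.4), and Section 13.7.8 refers to few subjects still on treatment. Schedule 2 is optional. That limits how often the change would be used. It does not remove the gap for Schedule 2, or for how Schedule 1 events are classified in the report.

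A reader might infer that an albuminuria DLT can never be counted, or that renal toxicity goes unwatched in cycle 1. The documents support neither, given the routes above.

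**Conclusion.** The point holds under two conditions: only scheduled collections are used, and the meeting is held when the DLT period ends. The confirmed event then arrives about 8 days late on either schedule (5–11 days on Schedule 1 and 7–9 on Schedule 2 across the dosing windows). A strict reader would exclude a nominal C2D1 value from the window altogether.

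The consequence is modest. When albuminuria is the cohort's only DLT, the recommendation was unchanged in 29 of 35 illustrative cases (31 of 35 with 0/3 just below). The 35-of-35 result might be read as showing that a late albuminuria DLT routinely misdirects escalation. It does not: it needs a second, different DLT in the same cohort, and it rests on assumed reference doses. The date arithmetic is certain; the model effect is illustrative only. Severity is minor to moderate, and the change is a cheap improvement.

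**What to change.** In Section 3.3.3, state that albuminuria of 2000 mg/24 hr or more on the pre-dose C2D1 collection is attributed to cycle 1, and that the confirmatory repeat may fall after Day 21 or Day 28. In Section 12.1, state that such a subject is carried as a pending DLT and that the N-CRM update and the escalation decision wait for the repeat.

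No scheduled collection is added. The cost is a delay of about one week to an escalation decision, only when a C2D1 value reaches the limit. Unless the cycle 2 dose is held, the repeat also reflects second-dose exposure, so some events may be charged to cycle 1 that one dose alone would not have sustained. That error is on the conservative side.

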3.3.4. Maximum Tolerated Dose

The MTD will be defined as that dose which has the highest probability of having a DLT rate within the target toxicity interval and for which the probability that the DLT rate lies within the excessive toxicity or the unacceptable toxicity window is less than 25%.

3.4. RP2 Dose and Administration Schedule Selection for Part 2

All available safety, PK, and PD data from the once every 3 weeks schedule, and if available, the once weekly dosing schedule, will be analyzed. If a consistent level of 95-100% receptor occupancy is observed in evaluable subjects at a dose lower than the determined MTD with no evidence of target mediated disposition in the PK profile and where emerging signs of clinical activity can be demonstrated, a dose level below MTD may be defined as the biologically effective dose (BED).

This lower dose level, or an intermediate dose considered the BED, may be tested as the RP2 dose for further evaluation in Part 2. Part 2 may start enrolling once Part 1 has

completed enrollment of Schedule 1 (once every three weeks) and after the preliminary PK and relevant PD data have been analyzed. The once weekly schedule may be explored prior to or in parallel with the expansion cohorts. Data considered will include, but not be limited to, relationships between safety and exposure, the PK profiles, as well as any emerging PD information, and early signs of clinical activity observed for each schedule evaluated in Part 1. If the once weekly schedule is explored prior to initiating Part 2, the chosen dosing regimen would need to provide evidence of the following in order to be the preferred schedule in Part 2: a better safety and tolerability profile at an equivalent or higher dose, or greater clinical activity, or a more desirable PK profile (i.e. no evidence of target-mediated disposition observed over the dosing interval). A preference might be given to the weekly schedule if at MTD1, the receptor occupancy levels are considered sub-optimal and/or saturation of soluble sBCMA is not maintained long enough on the every 3 weeks dosing schedule.

Part 2: Expansion Cohort:

(Note: For details on scheduled procedures in subjects given GSK2857916 in Part 2, refer to Time and Events Tables Section 7.1.2. The Time and Events Table for GSK2857916 administered to MM subjects on Schedule 1 is represented in Section 7.1.2.1, and the Time and Events Table for GSK2857916 administered to MM subjects on Schedule 2 is represented in Section 7.1.2.2. Refer to Time and Events Tables Section 7.1.2.3 and Section 7.1.2.4 for GSK2857916 administered to subjects with lymphomas on Schedule 1 or Schedule 2, respectively).

Once the RP2 dose and schedule have been selected, expansion cohorts will be enrolled in order to better characterize the safety profile of the selected dose and schedule.

- The Part 2 expansion will enroll up to 50 subjects as summarized below:
 - Multiple Myeloma cohort (up to 40 subjects)- no prospective screening of BCMA is required for enrollment
 - Futility analyses based on ORR will take place after approximately 15, 22 and 30 subjects have been evaluated for response. Full details can be found in Section 13.6.2
 - BCMA expression data and retrospective analysis will be performed on samples collected in the MM population
 - PRO will be collected via eDiary in the MM population in Part 2 only
 - BCMA positive lymphomas (defined as BCMA positive staining by IHC) (up to 10 subjects) – prospective screening of BCMA expression is required for enrollment
- Sparse PK sampling will be collected from all subjects in Part 2 to explore exposures of GSK2857916 at the RP2 dose (BED or MTD) and schedule. Genetics research

samples will also be collected as outlined in Section 7.6 and in the Time and Events Table in Section 7.1.2.

Note: For details on data dissemination and communication with sites (safety update meetings), refer to Section 12.1.

